14.1.18 Time to event variables

14.1.19 Progression-free survival

Usually in all Oncology studies, patients are followed for tumor progression after discontinuation of study medication for reasons other than progression or death. If this is not used, e.g. in Phase I or II studies, this should be clearly stated in the protocol. Note that

randomized trials (preferably blinded) are recommended where PFS is to be the primary endpoint.

Progression-free survival (PFS) is the time from date of randomization/start of treatment to the date of event defined as the first documented progression or death due to any cause. If a patient has not had an event, progression-free survival is censored at the date of last adequate tumor assessment.

14.1.20 Overall survival

All patients should be followed until death or until patient has had adequate follow-up time as specified in the protocol whichever comes first. The follow-up data should contain the date the patient was last seen alive / last known date patient alive, the date of death and the reason of death (“Study indication” or “Other”).

Overall survival (OS) is defined as the time from date of randomization/start of treatment to date of death due to any cause. If a patient is not known to have died, survival will be censored at the date of last known date patient alive.

14.1.21 Time to progression

Some studies might consider only death related to underlying cancer as an event which indicates progression. In this case the variable “Time to progression” might be used. TTP is defined as PFS except for death unrelated to underlying cancer.

Time to progression (TTP) is the time from date of randomization/start of treatment to the date of event defined as the first documented progression or death due to underlying cancer. If a patient has not had an event, time to progression is censored at the date of last adequate tumor assessment.

14.1.22 Time to treatment failure

This endpoint is often appropriate in studies of advanced disease where early discontinuation is typically related to intolerance of the study drug. In some protocols, time to treatment failure may be considered as a sensitivity analysis for time to progression. The list of discontinuation reasons to be considered or not as treatment failure may be adapted according to the specificities of the study or the disease.

Time to treatment failure (TTF) is the time from date of randomization/start of treatment to the earliest of date of progression, date of death due to any cause, or date of discontinuation due to reasons other than ‘Protocol violation’ or ‘Administrative problems’. The time to treatment failure for patients who did not experience treatment failure will be censored at last adequate tumor assessment.

14.1.23 Duration of response

The analysis of the following variables should be performed with much caution when restricted to responders since treatment bias could have been introduced. There have been reports where a treatment with a significantly higher response rate had a significantly shorter duration of

response but where this probably primarily reflected selection bias which is explained as follows: It is postulated that there are two groups of patients: a good risk group and a poor risk group. Good risk patients tend to get into response readily (and relatively quickly) and tend to remain in response after they have a response. Poor risk patients tend to be difficult to achieve a response, may have a longer time to respond, and tend to relapse quickly when they do respond. Potent agents induce a response in both good risk and poor risk patients. Less potent agents induce a response mainly in good risk patients only. This is described in more detail by [Morgan \(1988\)](#).

It is recommended that an analysis of all patients (both responders and non-responders) be performed whether or not a “responders only” descriptive analysis is presented. An analysis of responders should only be performed to provide descriptive statistics and even then interpreted with caution by evaluating the results in the context of the observed response rates. If an inferential comparison between treatments is required this should only be performed on all patients (i.e. not restricting to “responders” only) using appropriate statistical methods such as the techniques described in [Ellis et al \(2008\)](#). It should also be stated in the protocol if duration of response is to be calculated in addition for unconfirmed response.

For summary statistics on “responders” only the following definitions are appropriate. (Specific definitions for an all-patient analysis of these endpoints are not appropriate since the status of patients throughout the study is usually taken into account in the analysis).

Duration of overall response (CR or PR): For patients with a CR or PR (which may have to be confirmed) the start date is the date of first documented response (CR or PR) and the end date and censoring is defined the same as that for time to progression.

The following two durations might be calculated in addition for a large Phase III study in which a reasonable number of responders is seen.

Duration of overall complete response (CR): For patients with a CR (which may have to be confirmed) the start date is the date of first documented CR and the end date and censoring is defined the same as that for time to progression.

Duration of stable disease (CR/PR/SD): For patients with a CR or PR (which may have to be confirmed) or SD the start and end date as well as censoring is defined the same as that for time to progression.

14.1.24 Time to response

Time to overall response (CR or PR) is the time between date of randomization/start of treatment until first documented response (CR or PR). The response may need to be confirmed depending on the type of study and its importance. Where the response needs to be confirmed then time to response is the time to the first CR or PR observed.

Although an analysis on the full population is preferred, a descriptive analysis may be performed on the “responders” subset only, in which case the results should be interpreted with caution and in the context of the overall response rates, since the same kind of selection bias may be introduced as described for duration of response in [Section 14.1.23](#). It is recommended

that an analysis of all patients (both responders and non-responders) be performed whether or not a “responders only” descriptive analysis is presented. Where an inferential statistical comparison is required, then all patients should definitely be included in the analysis to ensure the statistical test is valid. For analysis including all patients, patients who did not achieve a response (which may have to be a confirmed response) will be censored using one of the following options.

- at maximum follow-up (i.e. FPFV to LPLV used for the analysis) for patients who had a PFS event (i.e. progressed or died due to any cause). In this case the PFS event is the worst possible outcome as it means the patient cannot subsequently respond. Since the statistical analysis usually makes use of the ranking of times to response it is sufficient to assign the worst possible censoring time which could be observed in the study which is equal to the maximum follow-up time (i.e. time from FPFV to LPLV)
- at last adequate tumor assessment date otherwise. In this case patients have not yet progressed so they theoretically still have a chance of responding

Time to overall complete response (CR) is the time between dates of start of treatment until first documented CR. Similar analysis considerations including (if appropriate) censoring rules apply for this endpoint described for the time to overall response endpoint.

14.1.25 Definition of start and end dates for time to event variables

Assessment date

For each assessment (i.e. evaluation number), the **assessment date** is calculated as the latest of all measurement dates (e.g. X-ray, CT-scan) if the overall lesion response at that assessment is CR/PR/SD/UNK. Otherwise - if overall lesion response is progression - the assessment date is calculated as the earliest date of all measurement dates at that evaluation number.

Start dates

For all “time to event” variables, other than duration of response, the randomization/ date of treatment start will be used as the start date.

For the calculation of duration of response the following start date should be used:

- Date of first documented response is the assessment date of the first overall lesion response of CR (for duration of overall complete response) or CR / PR (for duration of overall response) respectively, when this status is later confirmed.

End dates

The end dates which are used to calculate ‘time to event’ variables are defined as follows:

- Date of death (during treatment as recorded on the treatment completion page or during follow-up as recorded on the study evaluation completion page or the survival follow-up page).
- Date of progression is the first assessment date at which the overall lesion response was recorded as progressive disease.

- Date of last adequate tumor assessment is the date the last tumor assessment with overall lesion response of CR, PR or SD which was made before an event or a censoring reason occurred. In this case the last tumor evaluation date at that assessment is used. If no post-baseline assessments are available (before an event or a censoring reason occurred) the date of randomization/start of treatment is used.
- Date of next scheduled assessment is the date of the last adequate tumor assessment plus the protocol specified time interval for assessments. This date may be used if back-dating is considered when the event occurred beyond the acceptable time window for the next tumor assessment as per protocol (see [Section 14.1.26](#)).

Example (if protocol defined schedule of assessments is 3 months): tumor assessments at baseline - 3 months - 6 months - missing - missing - PD. Date of next scheduled assessment would then correspond to 9 months.

- Date of discontinuation is the date of the end of treatment visit.
- Date of last contact is defined as the last date the patient was known to be alive. This corresponds to the latest date for either the visit date, lab sample date or tumor assessment date. If available, the last known date patient alive from the survival follow-up page is used. If no survival follow-up is available, the date of discontinuation is used as last contact date.
- Date of secondary anti-cancer therapy is defined as the start date of any additional (secondary) antineoplastic therapy or surgery.

14.1.26 Handling of patients with non-measurable disease only at baseline

It is possible that patients with only non-measurable disease present at baseline are entered into the study, either because of a protocol violation or by design (e.g. in Phase III studies with PFS as the primary endpoint). In such cases the handling of the response data requires special consideration with respect to inclusion in any analysis of endpoints based on the overall response evaluations.

It is recommended that any patients with only non-measurable disease at baseline should be included in the main (ITT) analysis of each of these endpoints.

Although the text of the definitions described in the previous sections primarily relates to patients with measurable disease at baseline, patients without measurable disease should also be incorporated in an appropriate manner. The overall response for patients with measurable disease is derived slightly differently according to Table 14-4.

Table 14-4 Overall lesion response at each assessment: patients with non-target disease only

Non-target lesions	New Lesions	Overall lesion response
CR	No	CR
Non-CR/Non-PD ¹	No	Non-CR/non-PD
UNK	No	UNK
PD	Yes or No	PD

Non-target lesions	New Lesions	Overall lesion response
Any	Yes	PD

¹ As defined in [Section 14.1.8](#).

In general, the **non-CR/non-PD response** for these patients is considered equivalent to an SD response in endpoint determination. In summary tables for best overall response patients with only non-measurable disease may be highlighted in an appropriate fashion e.g. in particular by displaying the specific numbers with the non-CR/non-PD category.

In considering how to incorporate data from these patients into the analysis the importance to each endpoint of being able to identify a PR and/or to determine the occurrence and timing of progression needs to be taken into account.

For ORR it is recommended that the main (ITT) analysis includes data from patients with only non-measurable disease at baseline, handling patients with a best response of CR as “responders” with respect to ORR and all other patients as “non-responders”.

For PFS, it is again recommended that the main ITT analyses on these endpoints include all patients with only non-measurable disease at baseline, with possible sensitivity analyses which exclude these particular patients. Endpoints such as PFS which are reliant on the determination and/or timing of progression can incorporate data from patients with only non-measurable disease.

14.1.27 Sensitivity analyses

This section outlines the possible event and censoring dates for progression, as well as addresses the issues of missing tumor assessments during the study. For instance, if one or more assessment visits are missed prior to the progression event, to what date should the progression event be assigned? And should progression event be ignored if it occurred after a long period of a patient being lost to follow-up? It is important that the protocol and RAP specify the primary analysis in detail with respect to the definition of event and censoring dates and also include a description of one or more sensitivity analyses to be performed.

Based on definitions outlined in [Section 14.1.25](#), and using the draft FDA guideline on endpoints (Clinical Trial Endpoints for the Approval of Cancer Drugs and Biologics, April 2005) as a reference, the following analyses can be considered:

Table 14-5 Options for event dates used in PFS, TTP, duration of response

Situation		Options for end-date (progression or censoring) ¹ (1) = default unless specified differently in the protocol or RAP	Outcome
A	No baseline assessment	(1) Date of randomization/start of treatment ³	Censored
B	Progression at or before next scheduled assessment	(1) Date of progression (2) Date of next scheduled assessment ²	Progressed Progressed
C1	Progression or death after exactly one missing assessment	(1) Date of progression (or death) (2) Date of next scheduled assessment ²	Progressed Progressed

Situation		Options for end-date (progression or censoring) ¹ (1) = default unless specified differently in the protocol or RAP	Outcome
C2	Progression or death after two or more missing assessments	(1) Date of last adequate assessment ² (2) Date of next scheduled assessment ² (3) Date of progression (or death)	Censored Progressed Progressed
D	No progression	(1) Date of last adequate assessment	Censored
E	Treatment discontinuation due to 'Disease progression' without documented progression, i.e. clinical progression based on investigator claim	(1) N/A (2) Date of discontinuation (visit date at which clinical progression was determined)	Ignored Progressed
F	New anticancer therapy given	(1) Date of last adequate assessment (2) Date of secondary anti-cancer therapy (3) Date of secondary anti-cancer therapy (4) N/A	Censored Censored Event Ignored
G	Deaths due to reason other than deterioration of 'Study indication'	(1) Date of last adequate assessment	Censored (only TTP and duration of response)

¹.=Definitions can be found in [Section 14.1.25](#)
².=After the last adequate tumor assessment. "Date of next scheduled assessment" is defined in [Section 14.1.25](#).
³.=The rare exception to this is if the patient dies no later than the time of the second scheduled assessment as defined in the protocol in which case this is a PFS event at the date of death.

The primary analysis and the sensitivity analyses must be specified in the protocol. Clearly define if and why options (1) are not used for situations C, E and (if applicable) F.

Situations C (C1 and C2): Progression or death after one or more missing assessments: The primary analysis is usually using options (1) for situations C1 and C2, i.e.

- (C1) taking the actual progression or death date, in the case of only one missing assessment.
- (C2) censoring at the date of the last adequate assessment, in the case of two or more consecutive missing assessments.

In the case of two or missing assessments (situation C2), option (3) may be considered jointly with option (1) in situation C1 as sensitivity analysis. A variant of this sensitivity analysis consists of backdating the date of event to the next scheduled assessment as proposed with option (2) in situations C1 and C2.

Situation E: Treatment discontinuation due to 'Disease progression' without documented progression: By default, option (1) is used for situation E as patients without documented PD should be followed for progression after discontinuation of treatment. However, option (2) may be used as sensitivity analysis. If progression is claimed based on clinical deterioration instead of tumor assessment by e.g. CT-scan, option (2) may be used for indications with high early progression rate or difficulties to assess the tumor due to clinical deterioration.

Situation F: New cancer therapy given: the handling of this situation must be specified in detail in the protocol. However, option (1), i.e. censoring at last adequate assessment may be used as a default in this case.

Additional suggestions for sensitivity analyses

Other suggestions for additional sensitivity analyses may include analyses to check for potential bias in follow-up schedules for tumor assessments, e.g. by assigning the dates for censoring and events only at scheduled visit dates. The latter could be handled by replacing in [Table 14-5](#) the “Date of last adequate assessment” by the “Date of previous scheduled assessment (from baseline)”, with the following definition:

- **Date of previous scheduled assessment (from baseline)** is the date when a tumor assessment would have taken place, if the protocol assessment scheme was strictly followed from baseline, immediately before or on the date of the last adequate tumor assessment.

In addition, analyses could be repeated using the Investigators’ assessments of response rather than the calculated response. The need for these types of sensitivity analyses will depend on the individual requirements for the specific study and disease area and have to be specified in the protocol or RAP documentation.

14.1.28 Data handling and programming rules

The following section should be used as guidance for development of the protocol, data handling procedures or programming requirements (e.g. on incomplete dates).

14.1.29 Study/project specific decisions

For each study (or project) various issues need to be addressed and specified in the protocol or RAP documentation. Any deviations from protocol must be discussed and defined at the latest in the RAP documentation.

The proposed primary analysis and potential sensitivity analyses should be discussed and agreed with the health authorities and documented in the protocol (or at the latest in the RAP documentation before database lock).

14.1.30 End of treatment phase completion

Patients **may** voluntarily withdraw from the study treatment or may be taken off the study treatment at the discretion of the investigator at any time. For patients who are lost to follow-up, the investigator or designee should show "due diligence" by documenting in the source documents steps taken to contact the patient, e.g., dates of telephone calls, registered letters, etc.

The end of treatment visit and its associated assessments should occur within 7 days of the last study treatment.

Patients may discontinue study treatment for any of the following reasons:

- Adverse event(s)
- Lost to follow-up
- Physician decision
- Pregnancy

- Protocol deviation
- Technical problems
- Subject/guardian decision
- Death
- Progressive disease
- Study terminated by the sponsor
- Non-compliant with study treatment
- No longer requires treatment
- Treatment duration completed as per protocol

14.1.31 End of post-treatment follow-up (study phase completion)

End of post-treatment follow-up visit will be completed after discontinuation of study treatment and post-treatment evaluations but prior to collecting survival follow-up.

Patients may provide study phase completion information for one of the following reasons:

- Adverse event
- Lost to follow-up
- Physician decision
- Pregnancy
- Protocol deviation
- Technical problems
- Subject/guardian decision
- Death
- New therapy for study indication
- Progressive disease
- Study terminated by the sponsor

14.1.32 Medical validation of programmed overall lesion response

As RECIST is very strict regarding measurement methods (i.e. any assessment with more or less sensitive method than the one used to assess the lesion at baseline is considered UNK) and not available evaluations (i.e. if any target or non-target lesion was not evaluated the whole overall lesion response is UNK unless remaining lesions qualified for PD), these UNK assessments may be re-evaluated by clinicians at Novartis or external experts. In addition, data review reports will be available to identify assessments for which the investigators' or central reader's opinion does not match the programmed calculated response based on RECIST criteria. This may be queried for clarification. However, the investigator or central reader's response assessment will never be overruled.

If Novartis elect to invalidate an overall lesion response as evaluated by the investigator or central reader upon internal or external review of the data, the calculated overall lesion response

at that specific assessment is to be kept in a dataset. This must be clearly documented in the RAP documentation and agreed before database lock. This dataset should be created and stored as part of the 'raw' data.

Any discontinuation due to 'Disease progression' without documentation of progression by RECIST criteria should be carefully reviewed. Only patients with documented deterioration of symptoms indicative of progression of disease should have this reason for discontinuation of treatment or study evaluation.

14.1.33 Programming rules

The following should be used for programming of efficacy results:

14.1.34 Calculation of 'time to event' variables

Time to event = end date - start date + 1 (in days)

When no post-baseline tumor assessments are available, the date of randomization/start of treatment will be used as end date (duration = 1 day) when time is to be censored at last tumor assessment, i.e. time to event variables can never be negative.

14.1.35 Incomplete assessment dates

All investigation dates (e.g. X-ray, CT scan) must be completed with day, month and year.

If one or more investigation dates are incomplete but other investigation dates are available, this/these incomplete date(s) are not considered for calculation of the assessment date (and assessment date is calculated as outlined in [Section 14.1.25](#)). If all measurement dates have no day recorded, the 1st of the month is used.

If the month is not completed, for any of the investigations, the respective assessment will be considered to be at the date which is exactly between previous and following assessment. If a previous and following assessment is not available, this assessment will not be used for any calculation.

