7.1 Study flow and visit schedule

[Table 7-1](#) lists all of the assessments and indicates with an “X”, the visits when they are performed. All data obtained from these assessments must be supported in the patient’s source documentation.

No CRF will be used as a source document.

Screening/baseline evaluations must be performed \leq 21 days before Cycle 1 Day 1. Assessments required on Cycle 1 Day 1 that are performed as part of the screening evaluations and within 4 days prior to the first dose of study treatment, do not need to be repeated on Cycle 1 Day 1 (except Pregnancy test which needs to be completed within 72 hours prior to the first dose). Laboratory and radiological assessments performed as part of standard of care prior to signing informed consent may be used if performed within the screening time window.

During the course of the study visits, test and/or procedures should occur on schedule whenever possible. A visit window of +/- 4 days is allowed for visits and a window of +/- 7 days is allowed for radiological assessments.

For the 30-day and 150-day safety follow-up visits, a window of +7 days is allowed. For the 60-day, 90-day, and 120-day safety follow-up, a window of \pm 14 days is allowed.

If the infusion of either study drug is delayed (see [Section 6](#)), the visit will be shifted accordingly.

Table 7-1 Visit evaluation schedule (Cycle Length is 21 days/ 3 weeks)

	Protocol Section	Screening					Cycle 3	Subsequent Cycles	End of study treatment (EoT)	Safety Follow up
			Cycle 1		Cycle 2					
Visit Name		1	2	3	4	5	6	7,8,9...		
Day of cycle			1	8	1	8	1	1		30, 90, & 150 60 & 120
Adverse events	8.1	Continuous								
Prior/concomitant medications	6.4	Continuous								
Surgical and medical procedures		Continuous								
Study Drug administration LAG525(Q3W)	6.1		x		x		x	x		
Study Drug Administration PDR001(Q3W)	6.1		x		x		x	x		
Imaging and radiological tumor assessment	7.2.1	x			Every 6 weeks starting at week 12 through week 24 and every 12 weeks thereafter					
Serum prostate-specific antigen (PSA) (Prostate cancer only)	7.2.1.1.1	x			Every 6 weeks starting at week 12 through week 24 and every 12 weeks thereafter					
Cancer Antigen-125 (ovarian cancer only)	7.2.1.1.2	x			Every 6 weeks starting at week 12 through week 24 and every 12 weeks thereafter					
Measurement of superficial disease (if present)	7.2.1.1.3	x			Every 6 weeks starting at week 12 through week 24 and every 12 weeks thereafter					

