7.2.1.1 Radiological Tumor Assessment

At screening, all patients will undergo CT with i.v. contrast of the chest, abdomen and pelvis. Additionally, patients with lymphoma will also undergo CT with i.v. contrast of the neck and a PET scan. MRI should only be used to evaluate sites of disease that are not adequately imaged by CT. If a patient is intolerant of iodine-based contrast agents, CTs may be performed without contrast. MRI may be used to evaluate sites of disease where a CT without i.v. contrast is not adequate. Visible skin lesions and easily palpable subcutaneous tumors may be measured by physical examination using a ruler or calipers. Ultrasound should not be used to measure sites of disease.

No modality change would be allowed during the study when assessing overall tumor status. For subsequent scans in the same patient, the radiologist must account for all lesions that were present at screening and must use the same technique as used at screening. If possible, a single radiologist should perform all tumor response evaluations for an individual patient. Only in exceptional cases when during the study a patient develops intolerance to the CT scan contrast medium, a CT scan without contrast will be acceptable to avoid modality change.

Tumor assessments will be performed at the time points specified in [Table 7-1](#).

Radiological disease assessments will be performed every 6 weeks (± 7 days), starting 12 weeks after first dose of study drug and continuing through week 24. The frequency of radiological disease assessments will be reduced to every 12 weeks after patients have completed 24 weeks on treatment and will continue until confirmed disease progression. Solid tumor response will be determined locally according to RECIST 1.1 (Appendix 1). Lymphoma response will be determined locally according to Revised Response Criteria for Malignant Lymphoma, (Cheson et al 2007) (Appendix 2).

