14.1.36 Incomplete dates for last known date patient alive or death

All dates must be completed with day, month and year. If the day is missing, the 15th of the month will be used for incomplete death dates or dates of last contact.

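### The protocol's rules for incomplete scan and death dates misdate or drop results in uncommon cases, and the SAP neither adopts nor replaces them

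*Protocol*

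**What the plan says.** Protocol Appendix 1, section 14.1.35, requires complete scan dates and then gives fallbacks:

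- An incomplete date is set aside when another date at the same assessment is available.
- Missing day: "If all measurement dates have no day recorded, the 1st of the month is used".
- Missing month: the assessment is "considered to be at the date which is exactly between previous and following assessment".
- Missing month without both neighbours: "If a previous and following assessment is not available, this assessment will not be used for any calculation".

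For deaths, section 14.1.36 says "the 15th of the month will be used for incomplete death dates or dates of last contact", with no lower bound.

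Section 14.1.28 calls this material guidance. Section 14.1.33 introduces the rules as the ones to program efficacy results with, and 14.1.1 expects the analysis plan to refer to them.

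The scan schedule in Table 7-1 is "Every 6 weeks starting at week 12 through week 24 and every 12 weeks thereafter", and section 7.1 adds that "a window of +/- 7 days is allowed for radiological assessments". Under section 7.2.1.1 the frequency is "reduced to every 12 weeks after patients have completed 24 weeks on treatment and will continue until confirmed disease progression". Section 10.4 requires CR and PR in solid tumors to be confirmed at least 4 weeks after first observation.

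The SAP does not cite 14.1.35 or 14.1.36. SAP 2.1 says there is no imputation of missing data. SAP 5.1 covers dose end dates, adverse event and medication dates, and diagnosis and recurrence dates, but not scan or death dates.

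**The concern.** Followed as written, the rules give wrong answers in four situations: a progression scan that is the last scan, a week-24 scan between unequal gaps, a confirming scan without a day, and a death late in a month. Each can change a patient's outcome or event date. The primary population is 10 patients per cohort before expansion and at most 24 after it (Appendix 4, section 3), so one reclassified patient is visible. Because the SAP is silent on these dates and also rules out imputation in general terms, two programmers could handle the same record differently and both claim to follow the plan.

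**Working it through.** The documents give no figure for these rules, so there is nothing to reproduce. The check applies each rule to the planned schedule (weeks 12, 18, 24, 36, 48, each ±7 days) and the 28-day confirmation interval.

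**1. Month missing, no following scan.** The scan is dropped whatever it shows. Losing a final CR, PR or SD scan moves censoring back by one assessment, or removes a confirmation. Losing a progression scan deletes an event. What recovers it:

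| Endpoint | Recovery in the SAP |
|---|---|
| CBR (2.5.2) | Progression as reason for stopping treatment, or as cause of on-treatment death |
| PFS (2.7.1) | Progression as reason for stopping treatment; otherwise a later qualifying death |
| TTP (2.7.1) | None; censored at last adequate assessment |

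**2. Month missing, neighbours present.** The imputed date is the mean of the neighbours.

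- Week 24: (18 + 36)/2 = week 27, which is 21 days late. With ±7 days on both neighbours the range is (17 + 35)/2 = 26 to (19 + 37)/2 = 28, always outside week 24 ±1.
- Week 12: (0 + 18)/2 = week 9, if a baseline scan at day 0 counts as the previous assessment.
- Weeks 18, 36 and 48: unchanged, because their neighbours are equally spaced.

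**3. Day missing at the confirming scan only.** With true gap G and true day of month D, the imputed gap is G − (D − 1). Confirmation fails if this is below 28, that is, if D > G − 27. Counting days over a four-year calendar (1,461 days, 48 months):

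| True gap (days) | Fails if D is at least | Failing days | Share |
|---|---|---|---|
| 35 | 9 | 1,461 − 48×8 = 1,077 | 73.7% |
| 42 | 16 | 1,461 − 48×15 = 741 | 50.7% |
| 49 | 23 | 1,461 − 48×22 = 405 | 27.7% |
| 56 | 30 | 72 | 4.9% |
| 77 to 91 | never | 0 | 0% |

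With both scans uniform in their windows around a 42-day gap, the average is again 50.7%. If both scans lack the day and are at least 35 days apart, they lie in different months; the two 1sts are then at least 28 days apart, so none fail. For comparison, using the 15th at a 42-day gap fails only when D is 30 or 31: 72/1,461 = 4.9%.

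**4. Death with a missing day.** A patient scanned on the 20th who dies on the 28th of the same month is dated dead on the 15th, five days before the scan.

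**Weight of one patient.** 1/10 = 10 points of CBR; 1/24 = 4.2 points.

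**The case against.** The strongest reply is that these situations are rare and mostly harmless. Much of that stands.

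- Dates must be complete, missing values are queried (protocol 9.4), and each lesion has its own scan date (14.1.9). Another complete date at the assessment usually avoids the rule. However, 14.1.35 is not clear on this: its month clause is triggered by a missing month at any investigation, while its opening clause sets incomplete dates aside.
- A reader might infer that the rule singles out progression. It does not: any last scan is dropped. A progression scan can also have a successor, because treatment beyond progression is allowed (7.1.4) and scanning runs to confirmed progression. What is unequal is the consequence.
- A reader might infer that the shift to week 27 distorts the primary result. Under SAP 2.5.2 it rarely does. The shift needs a later scan, and SD or confirmed response at week 12 or 18 already counts. It matters under the week-24 landmark in protocol 10.4.1. A week-12 scan moved to week 9 still clears the 6-week minimum for SD in 14.1.17.
- A reader might infer that half of all confirmations are at risk. The figure applies only to 6-week gaps where the confirming scan alone lacks every day, and a later scan can still confirm.
- Loss of CBR through failed confirmation depends on SAP 2.5.3, which treats unconfirmed responses as non-response. Under 14.1.17 a single PR after 6 weeks would be SD, which SAP 2.5.2 counts as benefit. The loss of ORR under SAP 2.7.3 does not depend on that choice.

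The uncertainty over whether 14.1.35 applies at all is itself a reason to settle the rule in writing.

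**Conclusion.** The point holds as a faulty fallback rule with limited reach. Applied as written, it can delete a progression event (unrecovered for TTP, partly recovered for CBR and PFS), date a week-24 scan at about week 27, fail about half of valid 6-week confirmations when only the confirming scan lacks its day, and date a death before the last scan or dose. The SAP leaves open whether any of this applies.

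The percentages assume that scans follow the planned schedule and that calendar days are equally likely. The documents give no frequency of incomplete dates, so the overall effect cannot be sized; it is probably a few patients at most. The documents do not support a claim of systematic bias in CBR.

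**What to change.** State in SAP 5.1 that the following replaces protocol 14.1.35 and 14.1.36 for efficacy dates:

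- **No discarding:** a documented progression is never dropped.
- **Missing month:** use the nominal visit date. For an unscheduled scan, use a date consistent with the recorded parts. Bound either by the adjacent known assessments and by the end-of-treatment or last-contact date.
- **Missing day:** use the 15th, with the same bounds.
- **Confirmation:** when a date is imputed, judge the 4-week interval by scheduled visit. Two in-window visits 6 weeks apart are at least 42 − 14 = 28 days apart, so this does not relax the rule.
- **Deaths:** use the later of the 15th and the last date known alive.
- **Reporting:** give the number of imputed dates and say whether any CBR, ORR, PFS or TTP result changes.

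Appendix 1 is written for solid tumors, so the paragraph should say whether it also covers the DLBCL cohort.

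The cost is one paragraph, a small programming task and an entry in SAP section 4 as a change to the protocol-specified rule. No new data are needed. The SAP history already has an entry after database lock, so the timing of the change should be recorded; the affected dates can be counted from the existing database.
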